# 5.4.6.4 Treatment Compliance

Subjects will be instructed by study personnel on the importance of being compliant with the use of the study drugs and non-study products.

A dosing calendar will be provided to the subject with clear directions for completion at each dispensing visit (Section 5.1.1.2). Subjects will record daily use of topical study drug. Subjects will be instructed to return the dosing calendar and all study medication at each study visit, for review by study personnel in the presence of the subject.

The completed dosing calendar since the last visit will be collected, at each visit. The following guidelines pertain to treatment compliance assessment:

• Topical study drug (study cream): Treatment compliance will be assessed using the subject dosing calendar, and derived from the total expected doses and number of actual doses recorded in the dosing calendar (based on CRF data entries), over a given visit interval.

Inadvertent missed doses of topical study drug will be considered protocol deviations, as confirmed by discussions with the subject after reviewing the dosing calendar, and subjects should be appropriately counseled on the importance of following study drug dosing instructions.

Subjects should be reminded and encouraged to follow guidelines for non-study product use, throughout the study (Section 5.4.2 – Instructions for Use).

## 5.4.7 Method of Assigning Subjects to Treatment Groups

Upon signature of the ICF, each subject will be assigned a Subject Identification Number (SIN) to be used throughout the study. Once a SIN has been assigned, that number must not be used again for any other subject. Subjects may be re-screened once provided the reason for rescreening is not related to PIH severity (ODS), acne severity (IGA) or acne lesion counts.

Randomization will be stratified by study centers using the IRT system. Upon confirmation of subject eligibility, the IRT will be used to assign the blinded study drug. The randomization code will ensure the treatment assignment is random and is allocated in an overall ratio,

GALDERMA R&D RD.06.SPR.204245 V00 18AUG2021 Page 45 of 104

active to vehicle. Refer to Section 5.1.1 for an illustration of the study design and treatment allocation.

### **5.4.8 Dose Modification**

If a subject experiences persistent skin dryness or irritation, the Investigator may consider a reduced application frequency for the topical study drug in the first 4 weeks of the study, for a maximum duration of 2 weeks. Subjects should be instructed to capture all missed topical applications in the dosing calendar. Sites will record the timing and details of a prescribed dose reduction for topical medication in source records.

Signs and symptoms of local cutaneous irritation will be considered as Adverse Events if they are severe enough to lead to permanent discontinuation of topical study drug or if they require the use of concomitant treatment including OTC products (other than moisturizers). Refer to Section 6.3.4 for further details on local tolerability assessment.

## 5.4.9 Allocation Concealment and Blinding

Subjects will be centrally randomized using a system based on Interactive Response Technology (IRT). Allocation concealment will be ensured, as the system will not release the randomization code until the subject has been recruited into the trial, which takes place after all inclusion / exclusion criteria have been evaluated. Randomization will occur individually. The randomization code will be assigned to the unique Subject Identification Number (SIN) of each randomized subject and the simultaneous randomization of groups of subjects will be prevented.

All attempts will be made to keep the study site staff and subjects blinded to study treatment throughout the study. Members of the site staff will not have access to the randomized treatment assignment. Active study medications will have similar appearance, packaging and use instructions as the corresponding vehicle.

## 5.4.10 Unblinding During the Clinical Study

At the initiation of the study, site staff will be instructed on the method to follow for emergency breaking of the blind. The randomization information for any particular subject may be made available to the investigator in the event of a medical emergency or an AE that necessitates identification of the study drugs for the welfare of that participant. Whenever possible, the investigator should consult with the medical monitor and the Sponsor before breaking the blind, to discuss the decision. Emergency un-blinding during the clinical trial may be required for regulatory reasons (for expedited safety reporting).

When the blinding code is broken, the date and reason must be fully documented. The source note must also include a record of the discussion with the Medical Monitor. If the code is broken by the investigator, the subject must be withdrawn from the study after completing early termination procedures.

GALDERMA R&D RD.06.SPR.204245 V00 18AUG2021 Page 46 of 104

The Investigator has the sole responsibility for determining if unblinding of a subject's study treatment assignment is warranted. Subject safety must always be the first consideration in making such a decision. If the Investigator decides that unblinding is warranted, the Investigator should make every effort to contact the Medical Monitor prior to unblinding a subject's study treatment assignment unless this could delay emergency treatment of the subject. If this is not possible and the situation is an emergency the Principal Investigator or his delegated deputy may break the blind and contact the medical monitor as soon as possible thereafter. The applicable Sponsor standard operating procedure (SOP) will be followed for blind breaking

To avoid bias and to ensure the integrity of the blind, personnel directly involved with the ongoing conduct of the study from the Sponsor, CRO, or other investigational study centers will not have access to any information that may lead to unblinding

The randomization code will remain blinded to all study sites and study team members until completion of the study, and after the study database has been locked.

## 5.4.11 Non-Investigational Study Supplies

The Sponsor or designee will supply the following non-investigational supplies including:

- Cetaphil® Gentle Skin Cleanser
- Cetaphil® Dermacontrol Moisturizer SPF 30
- Cetaphil® Moisturizing Lotion

Alternative cleanser and moisturizers are not permitted, only the supplied non-investigational products above to be used. Refer to guidelines for using the cleanser and moisturizer (Section 5.4.2 – Instructions for Use). Topical retinoids are known to induce skin irritation and use of a moisturizer should minimize irritation and enhance compliance with using the topical study drug.

Upon receipt of non-investigational supplies, the site must conduct an inventory of all non-investigational supplies. If a damaged shipment is received and/or a temperature excursion has been experienced, the site will notify the Sponsor/CRO and follow the guidelines according to the current version of the pharmacy manual.

The investigator or designee should maintain records of non-investigational supplies received and dispensed. The monitor will confirm global accountability of non-investigational supplies (total received and dispensed).

Sites will be provided a stipend to locally source their own urine pregnancy test kits for use in the study.

GALDERMA R&D RD.06.SPR.204245 V00 18AUG2021 Page 47 of 104

### 5.4.12 Prior and Concomitant Therapy

### **5.4.12.1 Definition**

Information on previous and concomitant therapies will be collected and recorded in the CRF.

Previous therapies are defined as medications or procedures that have been stopped before the Screening visit and includes all acne therapies (within 6 months) and all other therapies (within 1 month).

Concomitant therapies are defined as:

- any existing therapies ongoing at the Screening visit,
- any changes to existing therapies (such as changes in dose or formulation) during the course of the clinical study, or
- any new therapies received by the subject since the Screening visit

Any new concomitant therapy or modification of an existing therapy may be linked to an adverse event (AE). A corresponding AE form must be completed to account for the change in therapy, except in some cases such as therapy used for prophylaxis, dose modification for a chronic condition, etc. In these cases, the medication will be linked to an item in the medical history.

## 5.4.12.2 Categories

The following two categories are to be considered for previous and concomitant therapies:

- Drugs/therapies including, but not limited to, prescription, over-the-counter (OTC), birth
  control pills/patches/hormonal devices, vitamins, cleansers, moisturizers, sunscreens, herbal
  medicines/supplements, and homeopathic preparations.
- Medical and surgical procedures including, but not limited to, laser/radiation procedures, dermal fillers, X-rays (excluding dental X-rays), etc.

### **5.4.12.3 Recording**

Previous and concomitant therapies are to be recorded on the Drugs/Therapies form (for drugs/therapies) and/or on the Medical and Surgical Procedures form (for medical/surgical procedures) in the case report form (CRF).

Concomitant therapies are to be recorded, reviewed, and updated at each visit. Every attempt should be made to keep concomitant therapy dosing and regimen constant during the trial.

Alternative cleanser and moisturizers are not permitted, only the supplied non-investigational products to be used.

7.0

GALDERMA R&D RD.06.SPR.204245 V00 18AUG2021 Page 48 of 104

# 5.4.12.4 Authorized Medication/Therapy

Unless specified as prohibited medication/therapy (see Section 5.4.12.5), all therapies are authorized, including the following as long as they are not indicated for the treatment of acne vulgaris.

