#### 3 BACKGROUND AND RATIONALE

## 3.1 Medical Background and Rationale

Acne is one of the most common skin disorders treated by dermatologists. While acne is highly prevalent in youth with around 85% of teenagers affected at some point in time. As shown in an epidemiological study (Alexis, 2007 and Canavan 2016) and by Halder and his group (Halder 1983) that the diagnosis of acne was the most common diagnosis in both light and white patients across all Fitzpatrick skin phototypes (1-VI) (Halder 1983, Kligman 1958, Taylor 2002, Pochi 1988, and Callender 2004). Post-inflammatory dyspigmentation in darker skin phototypes (IV-VI), often referred as hyperpigmentation (PIH). However, in patients with lighter Fitzpatrick Skin Types (I-III), the post-inflammatory dyspigmentation may be hyperpigmentation (PIH) and maybe discrete erythematous macules, post-inflammatory erythema (PIE), as any resolving cutaneous inflammatory process may have residual erythema or pigmentation. (Yoon-Soo 2013)

Acne may resolve with sequalae of PIH, PIE or atrophic scars. PIE is distinct from PIH because PIE describes residual erythema, while PIH describes subsequent pigment change. PIH can persist for months or years, causing considerable disfigurement and distress in the meantime. The psychological impact of PIH can be devastating, and many patients resort to extreme measures to try to eradicate it (Grimes 2006).

As acne is a chronic and relapsing disease normalizing follicular desquamation is then the key to achieve and maintain control of acne. Today it is established that retinoids such as trifarotene acts in the pathology of Acne vulgaris: they are a potent modulator of inflammation, cellular differentiation and keratinisation. Mechanistically, trifarotene binds to specific retinoic acid nuclear receptors (RAR- $\gamma$ ). Trifarotene is active and stable in keratinocytes but rapidly metabolized by human hepatic microsomes compared to other topical retinoids, leading to improved safety.

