## 4.2.1 Primary Efficacy Endpoint

[figure not shown]
Absolute change from Baseline in PIH Overall Disease Severity scores at Week 24

GALDERMA R&D RD.06.SPR.204245 V00 18AUG2021 Page 25 of 104

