#### **5.3.3** Exclusion Criteria

Subjects meeting any of the exclusion criteria are not eligible to participate in the study:

- 1. Subject with severe acne (IGA > 3),
- 2. Subject with more than 1 nodule/cyst on the face (excluding the nose),
- 3. Subject with acne conglobata, acne fulminans, secondary acne (chloracne, drug-induced acne, etc.), nodulocystic acne, acne requiring systemic treatment,
- 4. Subject with damaged facial skin (e.g. tattoo, skin abrasion, eczema or sunburned skin) that may interfere with study assessments,
- 5. Female subject who is pregnant, lactating or planning a pregnancy during the study,
- 6. Female subject of childbearing potential using combined oral contraceptives approved as acne treatments (e.g., Ortho Tri-Cyclen®, Yaz®, Diane-35®), in whom the dose has not been stable for at least 6 months prior to the Baseline visit,
- 7. Subject with known impaired hepatic or renal functions,
- 8. Subjects with a washout period for topical treatment or procedures on the face less than:

Topical treatments: Corticosteroids, antibiotics, benzoyl peroxide, azelaic acid, hydroxyacids, Zinc containing treatments, other anti-inflammatory drugs or other acne treatments (for example salicylic acid treatments/ transdermal contraceptives are forbidden if used to treat acne)	2 Weeks
Retinoids (including fixed drug combinations)	4 Weeks
Cosmetic/aesthetic procedures on the face (e.g., comedone extraction, desquamating, or abrasive agents, adhesive cleansing strips)	1 Week
Wax epilation	2 Weeks
Photodynamic therapy	6 Weeks
Laser therapy, microdermabrasion, deep chemical peel, plastic surgery for acne	3 months

9. Subject with a washout period for systemic treatment less than:

Corticosteroids, (except locally acting corticosteroids such as inhaled or intrathecal or dermal application at distance from the face), tetracyclines, other antibiotics (except penicillin)	1 month
Oral retinoids/isotretinoin	6 months

Cyproterone acetate / Chlormadinone acetate						
Spironolactone/ Drospirenone	3 months					
Immunomodulators	3 months					
Oral contraceptives for acne	1 month					

Note: No time frame period is specified for medicated shaving creams, after-shaves, colognes, astringents, or preparations with alcohol, but their application is prohibited during the study.

- 10. Subject with active or chronic skin allergies,
- 11. Subject with known or suspected allergy to the investigational product,

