## 5.4.12.5 Prohibited Medication/Therapy

Medications/therapies listed in Table 4 are prohibited during the study as they may interfere with efficacy and/or safety assessments.

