### Table 4: List of Prohibited Medications/Therapies During Study

### **Topical treatments on the face:**

- Corticosteroids, antibiotics, benzoyl peroxide, azelaic acid, alpha hydroxyl acids, salicylic acid, zinc containing treatments, other anti-acne treatments or other acne treatments (e.g., salicylic acid treatments)
- Retinoids
- Cosmetic/aesthetic procedures on the face (e.g., comedo extraction, desquamating or abrasive agents, adhesive pore cleansing strips)
- Wax epilation
- Photodynamic therapy
- Laser therapy, microdermabrasion, deep chemical peel, plastic surgery for acne
- Agents with potential drying effects on the skin: i.e. antibacterial soaps, astringents, other alcohol-containing topical preparations
- Use of tanning booths or lamps, as well as sunless tanning products for the duration

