#### Other:

Any drugs (topical or systemic) or procedures that are used off label for the treatment of acne vulgaris

GALDERMA R&D RD.06.SPR.204245 V00 18AUG2021 Page 50 of 104

If a prohibited therapy becomes necessary for the safety of the subject, the investigator should notify the medical monitor and discuss possible alternatives. If a subject receives a prohibited therapy during the clinical study (e.g., inadvertent short-term use), the investigator should also notify the medical monitor and discuss whether or not it is appropriate for the subject to continue receiving study drugs.

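### The washout and prohibited-therapy lists are built around acne and name no depigmenting class, so agents used for hyperpigmentation are not excluded from a trial whose primary endpoint is hyperpigmentation

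*Protocol*

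**What the plan says.** The primary endpoint (Protocol 4.2.1) is "Absolute change from Baseline in PIH Overall Disease Severity scores at Week 24". Section 5.4.12.5 gives the purpose of Table 4: the listed therapies "are prohibited during the study as they may interfere with efficacy and/or safety assessments".

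The lists themselves are:

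- **Topical washout (5.3.3, exclusion 8).** "Topical treatments: Corticosteroids, antibiotics, benzoyl peroxide, azelaic acid, hydroxyacids, Zinc containing treatments, other anti-inflammatory drugs or other acne treatments", with retinoids, cosmetic procedures, waxing, photodynamic therapy, laser and peels as further rows.
- **Systemic washout (5.3.3, exclusion 9).** Corticosteroids, antibiotics, oral retinoids, hormonal agents, immunomodulators and oral contraceptives for acne.
- **Prohibited facial topicals (Table 4).** "Corticosteroids, antibiotics, benzoyl peroxide, azelaic acid, alpha hydroxyl acids, salicylic acid, zinc containing treatments, other anti-acne treatments or other acne treatments", then retinoids, cosmetic procedures, tanning and sunless tanning products, and "Laser therapy, microdermabrasion, deep chemical peel, plastic surgery for acne".
- **Table 4 catch-all.** "Any drugs (topical or systemic) or procedures that are used off label for the treatment of acne vulgaris".

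The default for anything else is in 5.4.12.4: "Unless specified as prohibited medication/therapy (see Section 5.4.12.5), all therapies are authorized, including the following as long as they are not indicated" for acne vulgaris. Three supplied skin-care products are then listed as authorized on the treated areas. Sections 5.4.2, 5.4.11 and 5.4.12.3 bar alternative cleansers and moisturizers. Section 5.4.4 allows cosmetics in general, bars products with alcohol, alpha hydroxy or glycolic acids and astringents, and asks subjects to separate the study drug by about an hour from other permitted skin care products.

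**The concern.** A list meant to keep out therapies that interfere with the efficacy assessment should be organised around what is assessed. Here that is pigment, whereas every open-ended clause in the lists is about acne. A treatment used for hyperpigmentation that is not also an acne treatment or a named item passes through, and 5.4.12.4 makes that a permission rather than a silence.

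Use is plausible in this population. Section 3.1 says of post-inflammatory hyperpigmentation (PIH): "The psychological impact of PIH can be devastating, and many patients resort to extreme measures to try to eradicate it". A depigmenting agent started after Baseline acts on the primary endpoint itself. Subjects who see no improvement have more reason to start one. If trifarotene works, more of those subjects are on vehicle, and the treatment difference shrinks. The planned power of 90% leaves limited room for that.

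**Working it through.** **Step 1: does any clause reach a depigmenting agent as such?**

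| Clause | What it reaches | Hyperpigmentation use covered? |
|---|---|---|
| Exclusion 8, named items | Retinoids, azelaic acid, hydroxyacids, corticosteroids, laser, deep peel | Only where the agent is one of these |
| Exclusion 8, catch-all | Other anti-inflammatory drugs, other acne treatments | No |
| Exclusion 9 | Named systemic classes | No |
| Table 4, topical catch-all | Other acne treatments | No |
| Table 4, Other | Off-label use for acne | No |
| 5.4.12.4 qualifier | Therapies indicated for acne | No |
| 5.4.2, 5.4.11, 5.4.12.3 | Alternative cleansers and moisturizers | Only if the product is one of these |
| 5.4.4 | Alcohol, alpha hydroxy or glycolic acids, astringents; sunless tanning | Only where the product contains or is one of these |

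The protocol supplies its own example. Its reference list includes a randomized trial of a rucinol serum in melasma, and that product is on none of the lists.

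**Step 2: would use be recorded?** Section 5.4.12.1 asks for non-acne therapies stopped within 1 month before Screening. Footnote a to the assessment schedule (Protocol 5.1.1.2, repeated under SAP Table 1) says that only prior therapies that may bear on the inclusion or exclusion criteria should be recorded. A depigmenting agent bears on no criterion, so under the footnote recent prior use need not be captured. The two instructions conflict. Use during the study is recorded as concomitant therapy under either.

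**Step 3: would an analysis remove it?** The primary analysis is on all randomized subjects, so any use stays in. Of the four sensitivity analyses (SAP 4.10.2.2), copy reference, LOCF and observed case concern missing data. The PP set (Protocol 7.3.2, SAP 4.6) drops subjects with major deviations that could significantly affect efficacy, with use of prohibited medications as an example. Authorized use is not that.

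**Step 4: size, as illustration.** Inputs from Protocol 7.2: two-sided α 0.05, power 90%, difference 1.0, SD 1.4, dropout about 30%.

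The plan's figure reproduces: n = 2 × 1.4² × (1.960 + 1.282)² / 1.0² = 41.2, so 42 per arm; 42 / 0.70 = 60 randomized per arm, 120 in total. The two-sample t-test at 42 per arm has 89.9% power.

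Now let q be the net excess share of vehicle subjects who use an unlisted agent and g the ODS points each gains. The net difference is 1.0 − q × g. With g = 1 (an assumption, equal to the whole planned effect) and SD held at 1.4, the standard error is 1.4 × √(2/42) = 0.3055:

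| q (assumed) | Net difference | Difference / SE | Power, t-test | Power, normal approx. |
|---|---|---|---|---|
| 0 | 1.00 | 3.27 | 89.9% | 90.5% |
| 5% | 0.95 | 3.11 | 86.7% | 87.5% |
| 10% | 0.90 | 2.95 | 82.9% | 83.8% |
| 20% | 0.80 | 2.62 | 73.5% | 74.5% |

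Neither q nor g is in the documents.

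**The case against.** A reader might infer more than the text supports, and several of the objections stand.

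- **That the lists are acne-only.** They are not. They cover retinoids, which Section 5.2 itself describes as reducing epidermal melanin, together with azelaic acid, hydroxyacids, facial corticosteroids, laser, deep peels and tanning products. Exclusion 12 adds recent excessive UV exposure. The gap is what lies outside these items.
- **That any facial lightening product is openly allowed.** The three supplied products can be read as the only topicals permitted on the treated areas. But they follow the word *including*, nothing says *only*, and 5.4.4 presupposes other permitted skin care products. For facial topicals the text is ambiguous. That reading does not reach systemic agents or use before Baseline.
- **That use before Baseline biases the comparison.** Randomization should balance it between arms on average. It adds noise, not a systematic shift.
- **That use starting after Baseline is uncontrolled.** Section 5.4.12.3 asks that concomitant regimens be kept constant, and SAP 4.8 tabulates concomitant medications by arm. Recorded use would be visible. But the request to keep regimens constant would also favour continuing an agent already in use.
- **That no analysis could remove it.** Major deviations are defined in a separate specification that is not available here (SAP 4.5.3), and a meeting before unblinding decides exclusions (SAP 4.6). That meeting could act. Nothing in the plan tells it to.
- **That power is lost by a known amount.** More frequent use on vehicle is an inference. Section 5.2 notes some benefit from vehicle plus skin care in acne studies, which could weaken the motive. The risk concerns power and estimation; the documents do not point to a raised false-positive risk.

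**Conclusion.** The point holds in a limited form. The lists name no depigmenting class, their catch-alls and the 5.4.12.4 qualifier are tied to acne, and unlisted therapies are authorized by default. This conflicts with the stated purpose of Table 4 in a trial whose primary endpoint is PIH severity. It is clear for systemic agents during the study and for unlisted agents before Baseline, and ambiguous for leave-on facial topicals during the study.

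The expected consequence is extra variability and, if use after Baseline is commoner on vehicle, an attenuated treatment difference. Under the assumed 5% to 20% net excess use at one ODS point each, power would fall from about 90% to between about 87% and 73%. These figures show sensitivity and are not an estimate, because the documents give no usage rate and no effect per user. The PP analysis would not clearly remove such use, and recent prior use may go unrecorded. This is more than a missing detail, since following the plan as written admits a confounder of the primary endpoint.

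**What to change.** 1. Reconcile exclusions 8 and 9, Sections 5.4.12.3 and 5.4.12.4, the cosmetics text in 5.4.4 and Table 4 with the PIH endpoint, so that the lists and the qualifier in 5.4.12.4 address therapies indicated or used for hyperpigmentation as well as acne. Which agents are listed, and with what washout periods, is for the sponsor to decide.
2. State whether the three supplied products are the only topicals permitted on the treated areas.
3. Reconcile Section 5.4.12.1 with footnote a in both documents, so that use of such therapies before and during the study is recorded.
4. State in SAP 4.6 and the deviation specification that this use is a deviation relevant to the PP population, to be classified at the meeting before unblinding.

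The cost is a few lines of protocol and SAP wording; the sample size is unchanged. The small downside is that a few recent users must wash out or fail screening. Item 4 protects only the sensitivity analysis. The primary analysis is protected by keeping the use out in the first place.
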